13. STATISTICAL POWER AND SAMPLE SIZE ESTIMATION

Hypotheses for the Two-Group Randomized Control Trial Design: The aim is to conduct an RCT of the impact of CC versus MyP on patient-centered outcomes in up to eight community clinic sites in Long Beach. Participants will include: 150 patients randomly assigned to receive

Patterned after protocol published online in association with Appel et al. (2011)¹⁵

CC from trained health coaches, another 150 patients assigned to receive MyP from another group of trained health coaches over the course of 12 sessions in six months.

Intervention check: Does exposure to MyP versus CC lead to increased patient reports of fruit and vegetable intake in MyP? A preliminary check will be made to confirm that one of the defining features of the MyP approach, namely a doubling of F&V intake, was reflected in study participants' daily intake of F&V assessed at follow-up. If no difference were observed in F&V assessed at follow-up then the validity of the experimental contrast would be jeopardized. There could still be experimental effects, but the causal mechanisms would be unknown. Because numerous studies have succeeded in getting patients to double their intake of F&V for up to four years, a negative outcome of this intervention check is unlikely.²⁵

Question: Does exposure to MyP versus CC lead to decreased patient 12-months reports of daily hunger ratings/ daily meal satisfaction ratings/ daily fullness ratings in MyP during a time when patients were trying to lose excess weight (primary)? Will exposure to MyP versus CC lead to increased patient weight control self-efficacy, patient quality of life and patient satisfaction with her/his weight control program (primary)?

Question: Will exposure to MyP versus CC lead to increased weight loss/ reduced waist circumference equally for both conditions sustained for 12 months (secondary)?

Avoidance of bias. Covariates and effect modifiers. Standard demographic variables, including gender, age, ethnicity, marital status, and educational attainment will be included as covariates. Possible effect modifiers will also be included as covariates, including language preference (English / Spanish), last month food security, meal-skipping status, and daily physical activity level.

Sample size. (3) Statistical power. We power this proposal for the two-group (MyP vs CC) randomized design, setting alpha at 0.025 in order to have an experiment wise type I error rate of 0.05 after testing two hypotheses. Test of hypothesis #1 is therefore a test of the effect of MyP versus CC on the 12 months report of freedom from hunger measure used in the trial most similar to the trial proposed here.¹⁸³ The intervention effect size reported by Ello-Martin and associates is Cohen's $d = .52$. (Cohen's Effect Size = $(53.5 - 46.7) / 13.2 = .52$). The total sample sized needed to detect this effect, given a two-tailed critical $P = .025$, minimum statistical power of .80, and $\rho = .85$ the total sample size needed is approximately $N = 144$. The test of the second hypothesis is a test of MyP versus CC on the body weight lost over 12 months. We have three sources to draw on for estimating effect size involving weight loss over 12 months. The first is Ello-Martin and associates, whose low-fat, high fruit and vegetables intervention²⁰ was similar to but not identical to the DASH diet + (sat. fat & sugar restriction) featured in the current proposal.¹⁶ Ello-Martin's DASH-similar + fat restricted diet yielded a 12-months weight loss of 7.9 kg (SE=0.9, n=35) whereas the fat restriction-only condition yielded a 12-months weight loss of 6.4 kg (SE = 0.9, n=36). The total sample size needed to detect a similar 12-months weight loss difference at $\alpha=0.025$, $\text{power}=0.80$, $\rho = .7$ is $N= 206$ ($n=103$ per group). In Appel's recent clinical trial¹⁵ the in-person DASH-like dietary intervention yielded a 5.4 kg (SE=0.7, n=124) weight loss relative to baseline at 12 months follow-up.¹⁵ The body weight lost in response to Wadden's DPP-like dietary intervention¹⁴ was 3.4 kg (SE=0.6, n = 112) at 12 months follow-up¹⁸⁴ By design the protocols followed by Appel et al. (2011) and by Wadden et al. (2011) were similar, so comparing means across these two studies is informative. The sample size needed to detect this difference at 12 months at $\alpha = 0.025$, $\text{power}=0.80$, $\rho = .7$ is $N = 270$ ($n = 135$ per group). Based on the best available sources in the literature for information about reasonable estimates of the effect size to be expected and given an expected attrition of 20% at 6 month follow-up, the baseline initial sample of 300 (N=300 for 2 groups) appears to provide ample statistical power for the two experimental comparison hypotheses

Patterned after protocol published online in association with Appel et al. (2011)¹⁵

considered primary in this proposal. For a substudy involving only the 76% of participants who are Latino, the sample size (N =228) also yields acceptable statistical power. All additional hypothesis-testing will involve secondary hypotheses.

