Primary hypotheses: Compared to the CC approach, the MyP approach will yield better 12 months outcomes in terms of lower levels of everyday hunger, higher meal satisfaction, higher patient quality of life, higher patient self-efficacy at adhering to federal nutrition and physical activity recommendations, higher patient weight loss self-efficacy, and higher patient satisfaction with the weight loss program. **Secondary hypotheses:** Both intervention conditions will yield significant and similar declines in body weight and waist circumference; the MyP condition will yield greater reduction in systolic blood pressure than the CC condition.

PATIENT OUTCOMES (PROJECTED)

Patient-centered outcomes include: level of everyday hunger, health-related quality of life, self-efficacy to eat more fruits and vegetables as recommended on choosemyplate.gov, and patient satisfaction with the weight loss program, all of which are expected to favor the MyP condition at 12 months follow-up relative to the CC condition. Medical outcomes include changes in body

weight, waist circumference, and blood pressure. Body composition was expected to improve in both conditions but systolic blood pressure reduction was expected only in the MyP condition.

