2. SPECIFIC AIMS

We propose a randomized controlled trial (RCT) comparing the patient-centeredness and efficacy of two government-supported lifestyle change approaches to reducing patient obesity risk. Study participants are 261 obese, low income, mostly Latino and African American adult patients or staff associated with community health centers in Long Beach, California. The interventions will be implemented by trained community lifestyle change coaches (promotoras) with brief support from clinicians.

The first weight loss approach is the calorie-counting (CC), portion-cutting approach recommended at www.nutrition.gov. The second is the fill-up-sooner-on-fewer-calories approach found at www.choosemyplate.gov (MyP). The CC condition asks overweight patients to reduce their daily calorie intake to less than a recommended calorie target. The MyP approach also limits daily calories but emphasizes eating MORE high-satiety/ high-satiety foods by making ½ of daily food choices fruits and vegetables, and ¼ of daily food choices whole grains. MyP uses ipsative, progressive goal-setting to facilitate a doubling of usual fruit and vegetable intake. To facilitate adherence, the MyP approach also includes home environment changes to make healthier choices easier choices. All conditions encourage doing at least 150 minutes of moderate to vigorous physical activity a week.

Primary patient-centered outcomes include levels of everyday hunger, meal satisfaction, health-related quality of life, self-efficacy to eat more fruits and vegetables as recommended on choosemyplate.gov, and patient satisfaction with the weight loss program, all of which are expected to favor the MyP condition at 12 months follow-up relative to the CC condition. The primary medical outcomes are a reduction in body weight and waist circumference

Specific Aims

Aim #1. Use qualitative information from patients and clinical staff to revise intervention materials and procedures.

Aim #2. Use results of a pilot test of the intervention conditions to revise intervention materials and procedures.

Aim #3. Conduct a 12-months RCT involving two home visits, two group education classes, and seven telephone support/ lifestyle change coaching calls.

Aim #4. Obtain qualitative data from providers and coaches; combine with participant data to assess intervention feasibility, acceptability and perceived usefulness.

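### Section 13 controls error at 0.05 for two primary tests (12-month hunger and weight), but other current text names larger and different primary sets for which experiment-wise error is not controlled

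*Combined protocol and SAP*

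**What the plan says.** **Section 13, sample size text.** The error rule is explicit: "setting alpha at 0.025 in order to have an experiment wise type I error rate of 0.05 after testing two hypotheses". The first hypothesis is 12-month hunger and the second is 12-month weight loss, each MyP versus CC. The text closes with "All additional hypothesis-testing will involve secondary hypotheses". A two-tailed critical value is stated for hunger. The two weight calculations give alpha 0.025 without saying one- or two-sided.

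**Section 13, hypothesis questions.** Three outcomes are marked primary in one question: "daily hunger ratings/ daily meal satisfaction ratings/ daily fullness ratings in MyP during a time when patients were trying to lose excess weight (primary". The next question adds weight control self-efficacy and "patient quality of life and patient satisfaction with her/his weight control program (primary", which makes six. Weight and waist are then marked secondary: "Will exposure to MyP versus CC lead to increased weight loss/ reduced waist circumference equally for both conditions sustained for 12 months (secondary".

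**Section 1, Abstract.** The six primary hypotheses differ from those six. Fullness is absent, and self-efficacy for federal nutrition and activity recommendations appears. The list ends with "higher patient weight loss self-efficacy, and higher patient satisfaction with the weight loss program". Weight is under the secondary hypotheses: "Both intervention conditions will yield significant and similar declines in body weight and waist circumference".

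**Section 2, Specific Aims.** There are five primary patient-centered outcomes: "levels of everyday hunger, meal satisfaction, health-related quality of life, self-efficacy to eat more fruits and vegetables", plus program satisfaction. The primary medical outcomes are weight and waist. The primary medical hypotheses that follow concern weight and systolic blood pressure.

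**Section 8.** Hunger and weight are the primary pair, which agrees with the sample size text. However, the paragraph on choice of outcomes also lists weight among the secondary medical outcomes. The heading for the primary patient-centered outcome adds meal satisfaction and fullness as further satiety indicators.

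**Section 14** gives no multiplicity procedure and no rule on which list governs.

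**The concern.** The 0.05 guarantee belongs to a family of exactly two tests. Elsewhere in current text, including the same section, outcomes called primary have no alpha assigned, and one of the two tests that does have alpha, weight, is called secondary. An analyst who follows the Abstract or the hypothesis questions would report several primary results with no stated control over the set. An analyst who follows the sample size text would treat most of those results as secondary. What counts as confirmatory, and whether weight is included, would then be settled after the fact.

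A linked problem concerns the weight hypothesis itself. The sample size text sizes a between-arm difference. The Abstract, the Specific Aims and the hypothesis questions predict similar or equal loss and give no margin. A significant difference could be read as a primary success, and a non-significant one as confirming similarity, although non-significance does not show similarity.

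**Working it through.** **1. The plan's own figures.** Two tests at 0.025: bound 2 × 0.025 = 0.05, as stated; if independent, 1 − 0.975² = 4.9%. Hunger: d = (53.5 − 46.7)/13.2 = 0.515, rounded in the plan to 0.52. A two-sample t calculation with d = 0.52, two-sided 0.025 and 80% power gives 72 per arm, 144 in total, as stated (without using the stated ρ of 0.85).

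**2. Primary sets, side by side.**

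| Text | Outcomes labelled primary | Weight |
|---|---|---|
| Section 13, sample size | 2 | primary |
| Section 13, questions | 6 | secondary |
| Section 1 | 6 (a different six) | secondary |
| Section 2, outcomes | 5 + weight and waist | primary |
| Section 2, hypotheses | 5 + weight and systolic BP | primary |
| Section 8, choice of outcomes | 2 | primary and secondary |

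**3. Illustration for six outcomes.** No text states this test plan. Assume each of the six in the Section 13 questions is tested at two-sided 0.025 and any one significant result counts as success.
- Bound: 6 × 0.025 = 15%.
- Independent: 1 − 0.975⁶ = 14.1%.
- Equally correlated normal statistics, by numerical integration: 13.0%, 11.3%, 9.0% and 5.8% at r = 0.3, 0.5, 0.7 and 0.9. The documents give no correlations, so these are assumptions. The rate falls to 5% only at r of about 0.94.
- False claims favouring MyP only, 0.0125 per test, independent: 1 − 0.9875⁶ = 7.3%.
- If hunger, meal satisfaction and fullness count as one test, four remain: 1 − 0.975⁴ = 9.6% in either direction, if independent.
- If success required all outcomes, there would be no inflation.

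**4. Weight sample size, from the inputs in Section 13.** Year-long low-energy-density trial: difference 7.9 − 6.4 = 1.5 kg; SDs 0.9√35 = 5.32 and 0.9√36 = 5.40, root mean square 5.36; ρ = 0.7. The plan does not say how ρ enters; a variance factor 1 − ρ² = 0.51 is assumed.
- Formula: n per arm = 2(z₁ + z₂)²(SD/difference)²(1 − ρ²).
- Two-sided 0.025, 80% power: 2 × (2.241 + 0.842)² × (5.36/1.5)² × 0.51, about 124 per arm, 248 in total.
- Two-sided 0.05 or one-sided 0.025: 103 per arm, 206 in total, the stated figure.

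The second comparison, across the two primary care trials, has a difference of 5.4 − 3.4 = 2.0 kg. Its stated 135 per arm was not reproduced in any variant tried. At two-sided 0.025, the result was 123 to 124 per arm with factor 1 − ρ² and 145 to 146 with 2(1 − ρ).

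**5. Against the reduced sample.** 261 × 0.8 = 208.8, about 209 evaluable. Section 13 states the 20% attrition at 6 months; applying it at 12 months is an assumption. If 248 gives 80% power, 209 gives Φ(3.083 × √(209/248) − 2.241) = Φ(0.59), about 72%. The stated N of 270 exceeds 261 even with no loss. Hunger is not at risk: about 93% power at 209.

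**The case against.** The strongest defence is that the sample size text settles the matter. It limits the family to two tests, calls everything else secondary, and is supported by the named primary outcomes in Section 8. No passage claims 0.05 for the larger sets. This stands as far as it goes: for that family the error rate is controlled. It does not remove the explicit primary labels in the same section, the Abstract and the Specific Aims, and no text says which takes precedence.

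A reader might infer that the plan's stated 0.05 is false, or that the trial's false-positive rate is about 14%. The documents support neither. They give no test plan, success rule or correlations for the larger sets. Independence is the least plausible case, since hunger, meal satisfaction and fullness are described as indicators of one construct. The supportable statement is that error over those sets is not controlled.

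The double listing of weight in Section 8 should not carry much. The later statement of secondary medical outcomes there names BMI, waist and blood pressure without weight, so the earlier listing looks like a drafting slip.

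It is also fair that other repairs exist. Six primaries at 0.05/6 = 0.0083 would need 92 per arm for hunger, 184 in total, which is below 209. But the plan gives no effect sizes for the other patient-centered outcomes, and this route would discard the alpha split already written. A reader might also suspect that the lists were shaped by results. The documents do not show that: footnote 1 in Section 4 reports accrual and participant mix, not outcomes by arm.

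**Conclusion.** The concern holds as an inconsistency in primary-outcome labels that leaves the confirmatory set undefined. Under the sample size text in Section 13, 0.05 is controlled. For the sets in the Abstract, the Specific Aims and the Section 13 questions, it is not. The size is illustrative: at most 15% for six tests, and about 6% to 14% over the assumed correlations from 0.9 to zero, conditional on 0.025 per test and any one success counting.

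The weight hypothesis is also unsettled between difference and similarity, and its stated power should not be carried over to 261. It would be tempting to say that about 209 evaluable participants meet the stated 206. That does not follow at two-sided 0.025, where the plan's inputs give about 248 under the assumed variance factor. This should be fixed, but a coherent two-test plan already exists to fix it to.

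**What to change.** 1. Align the Abstract, the Specific Aims, the choice-of-outcomes paragraph and primary patient-centered outcome heading and text in Section 8, and the questions in Section 13 with the sample size text: 12-month hunger VAS and 12-month weight change as the only primary tests, at 0.025 each. State that the weight test is two-sided.
2. Label meal satisfaction, fullness, the self-efficacy measures, quality of life, autonomy, program satisfaction, waist, BMI and blood pressure as secondary. Either call them non-confirmatory or Holm-adjust them as their own family. The two primaries use the full 0.05, so Holm there controls error within that family only.
3. Remove weight from the secondary labels in Sections 1, 8 and 13.
4. State whether weight is tested for a between-arm difference or for similarity. A similarity claim needs a prespecified margin.
5. Recompute weight power for 261 from the Section 13 inputs at the stated alpha and sidedness, showing how ρ enters and what loss is assumed at 12 months.
6. Date these decisions relative to any look at outcomes by arm.

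The cost is small: no new data, mostly relabelling, one decision on the weight hypothesis and one restated power figure. The downside is that fewer outcomes can be called primary and the stated weight power becomes less favourable.

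### Holm's step-down would keep the 0.05 experiment-wise error of the two primary tests and add some power for weight; the Bonferroni split at 0.025 is valid but less efficient

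*Combined protocol and SAP*

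**What the plan says.** The sample-size text of section 13 powers the two-arm comparison by "setting alpha at 0.025 in order to have an experiment wise type I error rate of 0.05 after testing two hypotheses". The two hypotheses follow: "Test of hypothesis #1 is therefore a test of the effect of MyP versus CC on the 12 months report of freedom from hunger measure", and "The test of the second hypothesis is a test of MyP versus CC on the body weight lost over 12 months". The hunger calculation uses a two-sided 0.025 and 80% power and arrives at a total of about 144. The weight calculations give totals of 206 and 270 at the same stated alpha and power. The paragraph ends by treating these two comparisons as primary and all further testing as secondary. Section 8 agrees: it names everyday hunger as the primary patient-centred outcome and body weight as the primary medical outcome.

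Section 14 covers mixed models, missing data and intention-to-treat, but states no significance threshold, testing order or multiplicity procedure. The 0.025 in section 13 is therefore the only threshold in the document.

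Other places describe the primary set differently. The abstract and the question list in section 13 call several patient-centred outcomes primary and place weight among the secondary ones. Section 2 lists weight as a primary medical hypothesis but expects similar loss in both arms.

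**The concern.** A fixed 0.025 for each test never passes on the alpha released when one hypothesis is rejected. Suppose hunger gives p = 0.01 and weight p = 0.03. Under a fixed split weight is not claimed, although a procedure with the same 0.05 experiment-wise error would allow the claim. Weight is the test with less power to spare, and enrolment was reduced from 300 to 261, so the unused alpha falls where it would help most.

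**Working it through.** **1. The plan's figures.** The split is exact: 0.025 + 0.025 = 0.05 (1 − 0.975² = 0.0494 if the tests are independent). For hunger, n per arm = 2(z₀.₉₈₇₅ + z₀.₈₀)²/d² = 2(2.241 + 0.842)²/0.52² = 70.3, so 71 per arm. The t-based version gives 72 per arm, which is the plan's 144. The stated correlation of 0.85 is not needed to reach it.

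For weight, SD = SE × √n. The first source gives 0.9√35 = 5.32 and 0.9√36 = 5.40, with a difference of 7.9 − 6.4 = 1.5 kg. The plan does not say how its correlation of 0.7 enters. The ANCOVA factor 1 − 0.7² = 0.51 reproduces 206, but only at two-sided 0.05; at 0.025 it gives 248. I use that factor below.

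**2. Error control of Holm.** If both nulls are true, a false rejection needs the smaller p-value at or below 0.025, which has probability at most 0.025 + 0.025 = 0.05. If one null is true, its p-value must at least be at or below 0.05. The limit is therefore 0.05 for any correlation. Every Bonferroni rejection is kept.

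**3. Completers.** 300 × 0.8 = 240; 261 × 0.8 = 208.8, about 209. The 20% is stated for 6 months and is carried to 12 months here.

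**4. Power of each test on its own.** Noncentrality for hunger is 0.52√(n/2). For weight it is 1.5/√[(5.32² + 5.40²) × 0.51/n], with n per arm. Power is Φ(noncentrality − 2.241) at 0.025 and Φ(noncentrality − 1.960) at 0.05.

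| Completers | Test | Noncentrality | Power at 0.025 | Power at 0.05 |
|---|---|---|---|---|
| 240 | Hunger | 4.03 | 0.963 | 0.981 |
| 240 | Weight | 3.03 | 0.786 | 0.859 |
| 209 | Hunger | 3.76 | 0.935 | 0.964 |
| 209 | Weight | 2.83 | 0.722 | 0.808 |

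**5. Holm, independent tests.** Power for A = power of A at 0.025 + (gain of A from 0.025 to 0.05) × power of B at 0.025.

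- Weight, 240: 0.786 + (0.859 − 0.786) × 0.963 = 0.856.
- Weight, 209: 0.722 + (0.808 − 0.722) × 0.935 = 0.80.
- Hunger, 240: 0.963 + (0.981 − 0.963) × 0.786 = 0.977.
- Hunger, 209: 0.935 + (0.964 − 0.935) × 0.722 = 0.956.
- Both hypotheses: about 76% to 84% at 240, and 68% to 78% at 209.
- At least one: unchanged (about 99% and 98%), because Holm's first step is the Bonferroni criterion.

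**6. Sensitivity.** A simulation with correlation 0.3 between the tests gives almost the same weight figures (85.5% at 240, 80% at 209). The second weight source (2.0 kg difference) gives 79% to 86% and 73% to 81%. Without the 0.51 factor, weight goes from 47% to 58% and from 41% to 52%.

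**7. If the arms lose equal weight.** The chance of a false weight difference goes from 0.025 to 0.025 + 0.025 × 0.963 = 0.049 at 240 completers. Hunger power barely moves (96.3% to 96.4%).

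**The case against.** The strongest reply is that Bonferroni is valid and prespecified, judges each hypothesis without reference to the other, and has directly matching 97.5% intervals. Holm loses that match: an outcome rejected only at the second step can have a 97.5% interval that includes zero. This stands and should be stated as a cost.

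The 0.025 also sits in the sizing text, and Holm would leave it there. A reader might infer that the plan obliges the analyst to call a second p-value between 0.025 and 0.05 non-significant. That is the natural consequence of the split, but section 14 does not say it. What stands is that the analysis section lacks a rule and needs one.

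A reader might also infer that about 17% of the sample size is being wasted, since (1.960 + 0.842)²/(2.241 + 0.842)² = 0.826. That ratio compares unconditional tests at 0.05 and 0.025. Holm's second step is conditional and its first is still at 0.025, so no participants are saved.

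Finally, sections 1, 2 and 13 predict similar weight loss in the two arms, and then the gain disappears. This is correct as far as it goes. Yet section 13 also sizes weight as a between-arm difference of 1.5 to 2.0 kg, and the gain applies to that test if it is kept.

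**Conclusion.** Holm is an efficiency improvement over a valid procedure. The documents do not support the stronger reading that the plan gives up power for nothing: the fixed split has simpler intervals, hunger already has about 94% to 96% power, and the gain is conditional.

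If the assumed weight difference exists, Holm adds about 7 points of weight power at 240 completers and 8 at 209. At 209 this brings weight from below the plan's 80% target to about that target. If the arms do not differ in weight, Holm gives hunger essentially nothing and nearly doubles the error rate for the weight hypothesis alone, within the 0.05 family-wise limit.

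These sizes rest on SDs recovered from the quoted standard errors, the 0.51 factor, 20% loss at 12 months, between-test correlation of 0 to 0.3, and no allowance for clustering. The 0.51 factor is applied to SDs of weight change, so the absolute weight powers may be optimistic.

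**What to change.** First reconcile the primary family: the two hypotheses sized in section 13 against the longer primary lists in the abstract and in section 13's own questions. Holm over two p-values covers only two hypotheses; if a longer list is kept, apply Holm to that list.

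Keep 0.025 in the sample-size calculation. Then, before unblinded data are examined, add one sentence to section 14: for the two primary hypotheses, the smaller p-value is tested at 0.025 and, if significant, the larger at 0.05. Add that 97.5% intervals will be reported and may include zero for an outcome rejected only at the second step.

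Once the family is settled, the cost is this short addition, with no participants, no data and no loss of family-wise control. If results by arm have already been seen, the rule can no longer be presented as prespecified and the 0.025 split should stand.

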Prevention is far superior to a statistical cure, and every effort will be made to collect outcome data on all randomized participants. For example, we will ask medical staff at the clinical practices to obtain weight measurements on individuals who have stopped participating in the trial. Due to the high longitudinal correlation, missed "interior" visits won't decrease information very much for a linear trend. However, they are needed to assess departures from a linear trend. As detailed in Little and Rubin 2002¹⁹⁰ and discussed by Mealli,¹⁹¹ the underlying missing data process determines the biasing effects of missing data and structures valid analytic strategies. If data are missing completely at random, then there is no induced bias and a complete case analysis, while inefficient, is valid. Another approach to dealing with missing 12-months follow-up weights is to conduct "liberal" and "conservative" analyses. One would assume that on average there is neither weight loss nor gain, $[W_{12} - W_0 = 0]$.

Censoring

In certain analyses, data may be censored. Types of potential censoring include:

Patterned after protocol published online in association with Appel et al. (2011)¹⁵

1. Medical event censoring – a medical event (e.g. stroke, heart attack, or pregnancy), use of certain medications, or death. In this case, a weight may or may not be available. If available, the weight may be strongly influenced by the condition (e.g. extreme weight gain from use of oral steroids) such that the weight data should not be used subsequent to the event.
2. Dropouts not associated with a particular event (e.g., a participant refuses to continue). For our primary analysis we will use the weight change data for the pre-dropout period. Sensitivity analyses will evaluate the consequences of imputing subsequent weights using a statistical model, last-observation-carried-forward (equivalent to imputing 0 weight change subsequent to the dropout), or imputing a non-zero monthly weight gain subsequent to dropout.

Intent to Treat Analyses

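### Section 13 calls 300 ample for the weight hypothesis, but 300 less the expected 20% leaves 240, short of one of the plan's own two requirements (270); the later total of 261 leaves about 209

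*Combined protocol and SAP*

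**What the plan says.** Section 13 (Sample size) splits alpha into 0.025 for each of two hypotheses, hunger and 12-month weight loss, both treated as primary. For hunger it gives a total of 144.

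For weight it gives two totals, each at alpha 0.025, power 0.80 and rho 0.7:

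- First source, a single trial (losses of 7.9 and 6.4 kg): the total needed "is $N= 206$ ($n=103$ per group".
- Second source, a comparison across two trials. One arm "yielded a 5.4 kg (SE=0.7, n=124) weight loss relative to baseline at 12 months follow-up"; the other lost 3.4 kg (SE 0.6, n=112). The total needed "is $N = 270$ ($n = 135$ per group".

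It then reasons, "given an expected attrition of 20% at 6 month follow-up", that "the baseline initial sample of 300 (N=300 for 2 groups) appears to provide ample statistical power for the two experimental comparison hypotheses". For Latino participants alone it adds that "the sample size (N =228) also yields acceptable statistical power".

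Section 4 records that the total was later cut from 300 to 261. Its footnote 1 says that power for the subgroup analyses of women and Latinos still exceeded 80%. Section 14 (Missing and incomplete data) adds that "we will ask medical staff at the clinical practices to obtain weight measurements on individuals who have stopped participating in the trial".

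Sidedness is printed only in the hunger calculation: "given a two-tailed critical $P = .025".

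**The concern.** The attrition rate and the required totals stand in the same paragraph, but the paragraph never sets one against the other. Taking 20% off 300 gives a number below the larger requirement, so *ample* does not follow for that source. No power for weight is restated at 261.

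The two weight requirements also look inconsistent. They share alpha, power and rho and rest on almost the same standardised difference, yet they differ by 64 participants.

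The stake is interpretation. Section 2 expects weight loss to be significant in both arms and similar between them, and no margin for similarity is set. A reader told that the comparison is amply powered could take a non-significant difference as support for similarity.

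**Working it through.** **1. Convention check on hunger.** d = (53.5 − 46.7)/13.2 = 0.515. Per arm, n = 2(z₀.₉₈₇₅ + z₀.₈₀)²/d² = 2 × (2.2414 + 0.8416)²/0.515² = 71.6, so 72 per arm and 144 in total. The plan's figure reproduces at two-sided 0.025 with rho unused. Power is 96% with 240 analysed and 93% with 209.

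**2. Attrition against the plan's own weight totals.**

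- 300 × 0.80 = 240: above 206, below 270.
- 261 × 0.80 = 208.8: just above 206, below 270.
- 270/0.80 = 337.5, so 338 randomized would be needed. With 300, attrition could be at most 1 − 270/300 = 10%.
- 261 falls below 206 analysed once attrition exceeds 1 − 206/261 = 21%.

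**3. Power implied by those totals.** Suppose each printed N₀ gives 80% power at two-sided 0.025. Power at N is then Φ(3.0830 × √(N/N₀) − 2.2414).

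| Analysed | N₀ = 206 | N₀ = 270 |
|---|---|---|
| 240 | 86% | 75% |
| 208.8 | 81% | 68% |

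**4. Do 206 and 270 reproduce?** With SD = SE × √n:

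- First source: SDs 0.9√35 = 5.32 and 0.9√36 = 5.40; difference 1.5 kg; d = 0.280.
- Second source: SDs 0.7√124 = 7.79 and 0.6√112 = 6.35; difference 2.0 kg; d = 0.281.

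Per arm, n = (z_α + z_power)² × (SD₁² + SD₂²) × f/difference², where f is the variance factor for rho. With f = 1 − 0.7² = 0.51:

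- Two-sided 0.025: 9.505 × 57.51 × 0.51/2.25 = 123.9 and 9.505 × 101.08 × 0.51/4 = 122.5. Totals are 248 and 246.
- One-sided 0.025 (the same as two-sided 0.05): 102.3 and 101.2. Totals are 206 and 204.

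So with this factor 206 matches the one-sided calculation, and 270 matches neither.

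**5. Rounding.** Let each SE vary by ±0.05 and each difference by ±0.1. At two-sided 0.025 and f = 0.51 the total then runs from 194 to 317 (first source) and from 190 to 314 (second). One formula can give values close to both printed totals: a difference of 1.6 with SEs 0.88 and 0.87 gives 206; a difference of 1.95 with SEs 0.71 and 0.62 gives 269.

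**6. Power from the printed inputs.** The plan does not say how rho = 0.7 enters. Two-sided 0.025, range over the two sources:

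| Factor f | 240 analysed | 209 analysed |
|---|---|---|
| 1 (rho unused) | 47% | 41–42% |
| (1+rho)/2 = 0.85 | 54–55% | 48–49% |
| 2(1−rho) = 0.60 | 71–72% | 64–65% |
| 1−rho² = 0.51 | 79% | 72–73% |

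The middle two factors assume equal variances at baseline and 12 months. At one-sided 0.025 the full range is 58–86% at 240 and 52–81% at 209. Input rounding alone widens the two-sided 79% to 67–89%. The difference detectable with 80% power, two-sided, across the four factors is:

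- at 240: 1.5–2.1 kg (first source's SDs) or 2.0–2.8 kg (second's);
- at 209: 1.6–2.3 kg or 2.2–3.0 kg.

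**7. Subgroups at 20% attrition.** Footnote 1 reports 4.6% men, so women number 0.954 × 261 = 249, or 199 after attrition. Latinos number 0.76 × 261 = 198, or 159; the 76% share is an assumption here. The substudy's 228 (0.76 × 300) becomes 182. Hunger power is 92%, 84% and 89% respectively. Two-sided weight power is 39–70%, about 32–60% and 36–66%.

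**The case against.** The best defence is that the plan offers two requirements and 240 meets one of them with room to spare. If 206 is right, even 209 gives 81%. The one setting that reproduces 206 exactly, one-sided 0.025 with 1−rho², gives 86% at 240 and 81% at 209, and the documents do not print two-tailed for weight. This stands as far as it goes. However, alpha is stated once for both hypotheses and is two-tailed where sidedness is given, so two-sided is the likelier reading. The shortfall against 270 does not depend on sidedness.

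One might suppose that 270 already contains an attrition allowance. The sentence ties it only to alpha, power and rho, and attrition enters afterwards. In any case 261 is below 270.

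The count of 240 is a completer count. Section 14 plans to seek weights on people who stop, uses pre-dropout data and fits a longitudinal model, so the effective loss may be below 20%. Against that, the 20% is a 6-month rate, and no 12-month figure is given from which to judge the balance.

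The Abstract, and the list of questions in section 13, call weight secondary. Section 8 names it the primary medical outcome, and the power paragraph gives it half the alpha.

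Three stronger readings are tempting, and the documents do not support them:

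- *Power for weight is only 47%.* That figure needs two-sided testing, 20% loss at 12 months and rho unused, although rho is printed for both weight calculations. It is one end of a range. The SEs do appear to be of weight change, in which case 1−rho² may count the baseline correlation twice; the plan does not settle this.
- *206 and 270 cannot both be right.* Step 5 shows that rounding of the inputs could account for both.
- *The subgroup power statements are false.* Neither names an outcome, and both hold for hunger after 20% attrition.

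**Conclusion.** The point holds as a statement that needs correcting. *Ample* is supported for hunger, if d = 0.52, taken from repeated ratings over one year, applies at 12 months. For weight it is not supported by the plan's own figures: 240 and 209 both fall short of 270. At the planned total the shortfall is modest, about 5 points of power against one source and none against the other. At 261 it is about 12 points against the 270 source. These figures assume that each printed N gives 80% at two-sided 0.025 and that 20% is the loss at 12 months.

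Confidence is high for the 240-versus-270 arithmetic. It is lower for the non-reproduction of 206 and 270, which shows only that the inputs and method need to be stated and checked. The subgroup sentences are unclear rather than wrong. With 20% attrition they would not hold for weight under the two-sided calculations shown.

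**What to change.** In section 13, for weight:

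- (a) State the sidedness, the SD of change and how rho enters. Recheck 206 and 270 from those inputs and correct them if they do not reproduce.
- (b) State a 12-month attrition assumption, allowing for weights recovered from the clinics, and the number analysed that results from 300 and from 261.
- (c) Replace *ample* for weight with the power and detectable difference at both totals, by the one method stated in (a). Keep *ample* for hunger.
- (d) Add that a non-significant weight difference is not by itself evidence of similar weight loss.

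A minor addition: say which outcome and what attrition the subgroup statements in footnote 1 and the 228-person substudy sentence refer to.

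The cost is wording in section 13 and footnote 1. Enrolment, procedures and analysis do not change. The stated power for weight will probably read less favourably.
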